### **Pulmonary physiology**

To assess the impact of the IPs on pulmonary physiology, change from baseline to the end of treatment epoch (26 weeks of treatment) in DLCO and DLCO/Hb ([Brian L. Graham](#)) will be analyzed by fitting the same model of MMRM as described for the endpoint of change from baseline of FVC at 26 weeks (mL) in addition to summary statistics by treatment.

### **Exercise capacity**

To assess the impact of the IPs on exercise capacity, change from baseline to the end of treatment epoch (26 weeks of treatment) in 6-minute walk distance (the best of the two testing results) will be analyzed by fitting the same model of MMRM as described for the endpoint of change from baseline of FVC at 26 weeks (mL) in addition to summary statistics by treatment.

#### **2.6.1.2 Safety endpoints**

All listings and tables will be presented by treatment group.

Safety summaries (tables, figures) include only data from the on-treatment period with the exception of baseline data which will also be summarized where appropriate (e.g. change from baseline summaries). In addition, a separate summary for death including on treatment and post treatment deaths will be provided. In particular, summary tables for adverse events (AEs) will be summarized from initial treatment through the end of the Safety Follow-up.

The safety follow-up period will be a minimum of 30 days and may vary within each cohort. See Protocol Section 17 for details.

### **Adverse events**

All information obtained on adverse events will be displayed by treatment group and participant.

The number (and percentage) of participants with treatment emergent adverse events (events started after the first dose of study medication or events present prior to start of double-blind treatment but increased in severity based on preferred term) will be summarized in the following ways:

- by treatment, primary system organ class and preferred term.
- by treatment, primary system organ class, preferred term and maximum severity.
- by treatment, Standardized MedDRA Query (SMQ) and preferred term.

Separate summaries will be provided for study medication related adverse events, death, serious adverse events, other significant adverse events leading to dose suspension and/or discontinuation.

Any adverse events of special interest will be outlined in Protocol Section 17.

A participant with multiple adverse events within a primary system organ class is only counted once towards the total of the primary system organ class.

### **Vital signs**

All vital signs data will be listed by treatment group, subject, and epoch/visit/time and if ranges are available abnormalities (and relevant orthostatic changes) will be flagged. Summary statistics will be provided by epoch, treatment, and visit/time.

### **12-lead ECG**

All ECG data will be listed by treatment group, subject and epoch/visit/time, and abnormalities will be flagged. Summary statistics will be provided by epoch, treatment, and visit/time.

### **Clinical laboratory evaluations**

All laboratory data will be listed by treatment group, subject, and epoch/visit/time and if normal ranges are available, abnormalities will be flagged. Summary statistics will be provided by epoch, treatment, and visit/time. Shift tables using the low/normal/high/ (low and high) classification will be used to compare baseline to the worst on-treatment value.

#### **2.6.1.3 Patient reported outcomes**

L-IPF (Impacts and Symptoms Modules), K-BILD, Leicester cough, and R-Scale for IPF questionnaires score will be reported by treatment group, patients, and epoch/visit/time. Summary statistics on the change from baseline of PRO score at the end of the treatment epoch will be provided by treatment and visit time. For continuous PRO endpoints, if data allows, the endpoints will be analyzed by fitting the same model of MMRM as described for the endpoint of change from baseline of FVC at 26 weeks (mL) in addition to summary statistics by treatment.

#### **2.6.2 Statistical hypothesis, model, and method of analysis**

Refer to [Section 2.6.1.1](#) for the statistical hypothesis and model information for Efficacy and Pharmacodynamic secondary endpoints.

#### **2.6.3 Handling of missing values/censoring/discontinuations**

Missing data will not be imputed.

#### **2.6.4 Sensitivity analyses**

Not applicable.

#### **2.6.5 Supplementary analyses**

Not applicable.

### **2.7 Safety analyses**

Refer to [Section 2.6.1.2](#).

## **2.8 Pharmacokinetic endpoints**

Analyses of Pharmacokinetic endpoints will not be conducted due to the early termination of the study.

## **2.9 PD and PK/PD analyses**

Secondary efficacy and PD endpoints can be found in [Section 2.6.1.1](#).

## **2.10 Patient-reported outcomes**

Refer to [Section 2.6.1.3](#) for detailed analysis.

## **2.11 Biomarkers**

Soluble biomarker analysis will be excluded from the CSR and will be reported separately.

## **2.12 Other Exploratory analyses**

No analyses will be conducted on the exploratory objectives/endpoints except soluble biomarkers due to the early termination of the study.

Data generated on hypothesis-free platforms may be reported separately.

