Clinical features of IPF include progressive cough, dyspnea, restrictive ventilatory defect, and progressive fibrosis and destruction of the lung parenchyma ([Lynch et al 2016](#)). The diagnosis is made in patients with the appropriate clinical features and the histologic pattern of usual interstitial pneumonia (UIP) (based on lung biopsy or high-resolution computed tomography (HRCT)). Challenging factors for clinical management include older age, comorbid conditions, and acute unpredictable exacerbations. Acute exacerbations of IPF are defined as sudden (typically less than 30 days onset) unexplained worsening of underlying disease, including new radiological infiltrates (based on HRCT) or UIP pattern. The progressive deterioration of lung function results in respiratory failure. The prognosis following acute exacerbation and deterioration of lung function is poor, with 1-year and 5-year survival rates of 56.2% and 18.4% following acute exacerbation, which is considerably shorter than in IPF patients without acute exacerbation ([Song et al 2011](#)).

The underlying pathophysiology of IPF remains unknown and likely involves a complex interplay of several key factors including environmental exposures, cellular susceptibilities and aberrant repair process. It is believed that recurrent micro injuries to the alveolar epithelium over time leads to a maladaptive repair process, which is characterized by epithelial cell death, senescence and inappropriate re-epithelialization. In this setting, epithelial signaling leads to recruitment and activation of fibroblasts into myofibroblasts and recruitment of inflammatory cells. Additionally, failure of re-endothelialization may lead to a dysfunctional alveolar-capillary barrier, inducing an additional pro-fibrotic response ([du Bois 2010](#), [Sgalla et al 2018](#)). The ultimate proliferation and activation of fibroblasts and myofibroblasts and profibrotic immune cells leads to secretion of connective tissue matrix molecules, such as collagen, to replace the damaged tissue but also displaces healthy tissue leading to scarring and ultimately organ failure ([du Bois 2010](#)).

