6.7.2.2 Determination of IPF Exacerbation

Based on the results obtained from evaluations at the IPF Exacerbation Visit and/or the records obtained from a visit to another facility (if applicable), the investigator will determine whether an IPF exacerbation or suspected IPF exacerbation has occurred. The investigator will assess the occurrence of IPF exacerbation using the revised diagnostic criteria for IPF exacerbation and suspected IPF exacerbation of the international working group report in 2016 ([Collard et al 2016](#)), as follows:

- Acute worsening or development of dyspnea typically <1 month duration.
- Computed tomography with new bilateral ground-glass opacity and/or consolidation superimposed on a background pattern consistent with UIP pattern.
- Deterioration not fully explained by cardiac failure or fluid overload.

Note: Events that are clinically considered to meet the definition of acute exacerbation of IPF but fail to meet all diagnostic criteria owing to missing computed tomography data should be termed “suspected acute exacerbations.”

The investigator's determination of IPF exacerbation based on the 2016 definition should be documented on the appropriate CRF.

As noted, treatment for an acute exacerbation is at the discretion of the investigator and medications (such as prednisone) can be freely initiated or increased at the investigator's discretion.

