12.6 Analysis of exploratory endpoints

12.6.1 Efficacy and/or Pharmacodynamic endpoint(s)

Disease exacerbation

Time to IPF exacerbations or suspected exacerbations will be assessed using the statistical method mentioned in [Section 12.5.1](#) “Time to event analysis”. In addition, number and percentage of exacerbations will be summarized by epoch/visit/treatment.

Exploratory Progression-free survival (PFS)

Time to progression as defined by a composite endpoint including any of the following events:

- Absolute reduction from baseline of $\geq 5\%$ predicted in FVC
- Non elective hospitalization for respiratory events
- Lung transplant or death

Same statistical analysis specified in [Section 12.5.1](#) “Time to event analysis” will be applied to this endpoint.

Pulmonary imaging

Change from baseline to the end of treatment epoch (26 weeks of treatment) in quantitative high-resolution computed tomography (qHRCT) structural and functional metrics (interstitial fibrotic features) will be reported using summary statistics by treatment.

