| Exploratory objective(s)  | Endpoint(s) for exploratory objective(s)  |
| 

To assess the impact of the investigational products on disease exacerbation.

To assess the impact of the investigational products on additional "progression-free survival (PFS)" analysis

To evaluate change in extent of pulmonary fibrosis quantified by HRCT scan

To explore the impact of the investigational products on peripheral blood biomarkers

  | 

IPF exacerbations or suspected exacerbations as determined by investigator and by using modified diagnostic criteria derived from Collard et al 2016 and exacerbations as determined by the investigator as AEs/SAEs

Time to progression as defined by a composite endpoint including any of the following events:

Absolute reduction from baseline of <math>\geq 5\%</math> predicted in FVC

Non-elective hospitalization for respiratory events

Lung Transplant or Death

Change in fibrosis from baseline to the end of treatment epoch (26 weeks of treatment) in quantitative high-resolution computed tomography (qHRCT)

Change from baseline in soluble pharmacodynamic, target engagement and disease markers (may include but are not limited to: cci [REDACTED] and additional protein profiling) in the peripheral blood.

  |

| Objective(s)  | Endpoint(s)   |
|---|---|
| 

The pharmacokinetics of the investigational products after multiple doses will be assessed.

To explore the pharmacogenetics for the potential disease association or participant stratification

CCI

 | 

Appropriate PK parameters will be calculated where possible using non-compartmental analysis. These may include Tmax, Cmax, AUCs. Population PK modelling may also be used for parameter estimation.

DNA analysis at baseline

 |
|   |   |
|   |   |

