## **4 Change to protocol specified analyses**

Due to the decision of the early termination of the study, the following analyses will not be performed, therefore removed from the SAP:

1. The pooling of the placebos from different cohorts
2. All sensitivity and supplemental analyses for the primary endpoint
3. All the planned CSR analyses on exploratory objectives and endpoints stated in [Section 1.2](#)
4. Planned Interim Analyses

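### SAP 2.12 and Section 4 drop both exacerbation outputs planned in the protocol, so IPF exacerbations determined on the CRF are collected but not summarised by arm

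*SAP*

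**What the plan says.** Disease exacerbation is an exploratory endpoint in both documents. SAP Table 1-1 still defines it by two sources. One is criteria-based: "IPF exacerbations or suspected exacerbations as determined by investigator and by using modified diagnostic criteria derived from" the 2016 international working group report. The other is the safety reporting stream: "exacerbations as determined by the investigator as AEs/SAEs".

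Protocol 12.6.1 plans two outputs. The first reads "Time to IPF exacerbations or suspected exacerbations will be assessed using the statistical method mentioned in" Section 12.5.1, which is the Kaplan-Meier method. For the second, "number and percentage of exacerbations will be summarized by epoch/visit/treatment".

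Protocol 6.7.2.1 and Table 8-1 give the event its own visit, with spirometry, DLCO and imaging. Protocol 6.7.2.2 separates a full exacerbation from a suspected one (missing CT data) and adds: "The investigator's determination of IPF exacerbation based on the 2016 definition should be documented on the appropriate CRF".

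SAP 2.12 then states: "No analyses will be conducted on the exploratory objectives/endpoints except soluble biomarkers due to the early termination of the study". SAP Section 4 lists among the removed items "All the planned CSR analyses on exploratory objectives and endpoints stated in" SAP 1.2. The secondary efficacy analyses and the safety analyses stay in the SAP.

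**The concern.** The protocol asks sites for a structured assessment of each suspected exacerbation and a determination against named criteria. Under the SAP as written, nothing in the report uses that determination. A reader of the study report could not find out how many treated participants in each arm had an exacerbation that met the criteria, or a suspected one.

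The event matters in this disease. Protocol 1.1 describes a poor prognosis, "with 1-year and 5-year survival rates of 56.2% and 18.4% following acute exacerbation". An imbalance between arms, in either direction, is information that a reader of a terminated trial would want. The data to show it are already on the CRF.

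**Working it through.** The documents give no figure to reproduce. The check is to trace every place in the current SAP where an exacerbation could appear by arm.

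1. **Dedicated outputs.** Protocol 12.6.1 plans two: time to event, and number and percentage by treatment. Both belong to the exploratory endpoint in SAP Table 1-1, and SAP 2.12 and Section 4 cancel exploratory analyses. Retained: 2 − 2 = 0.

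2. **Exemptions.** SAP 2.12 exempts soluble biomarkers only, and SAP 2.11 sends those to a separate report. The wording of Section 4 is limited to CSR analyses, which might suggest that exacerbations could be reported elsewhere. SAP 2.12 closes that route by allowing no analysis of the other exploratory endpoints.

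3. **Route through PFS (SAP 2.6.1.1).** Non-elective respiratory hospitalisation is a PFS component. Acute exacerbation, definite or suspected, is the first example of a qualifying cause, as judged by blinded adjudicators. Components are summarised separately, and each is compared between arms by logistic regression if the data allow. There are three limits:
   - The component pools exacerbation with pulmonary infection, embolus, pneumothorax, aspiration and ARDS, so no exacerbation count results.
   - An exacerbation managed without admission, and meeting no other PFS component, is not counted.
   - The cause is the adjudicators' opinion on the hospitalisation, not the investigator's CRF determination.

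4. **Route through the AE tables (SAP 2.6.1.2).** Treatment-emergent AEs are tabulated by treatment, system organ class and preferred term, and also by severity and SMQ, with separate SAE and death summaries. An exacerbation reported as an AE appears under whatever preferred term is coded. The SAP has no rule linking the CRF determination to an AE term, names no SMQ or grouping for exacerbation, and does not carry over the definite or suspected status. Parts of Protocol 17.1 are blacked out, so I draw nothing from the absence of an exacerbation entry there.

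5. **Use of the CRF determination.** Steps 1 to 4 cover SAP 2.6.1.1, 2.6.1.2, 2.12 and 4. None of them uses it.

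6. **Precision.** The documents give no exacerbation rate and no number actually randomised. The planned arm size is 47 (Protocol 17.1.11.1). If a full arm of 47 had no events (an assumption for illustration only), the exact 95% upper limit would be 1 − 0.025^(1/47) = 7.5%. A smaller arm gives a wider limit. That supports a descriptive summary and not a test.

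**The case against.** The strongest reply is that exacerbations are not lost. Events with admission stay in a secondary endpoint that is compared between arms if data allow, and events reported as AEs or SAEs stay in by-arm tables. Protocol 10.1.1 asks for AEs to be recorded as a diagnosis where possible, and an exacerbation requiring inpatient admission would ordinarily be an SAE. This stands. A reader might infer from SAP 2.12 that every analysis of exacerbations is cancelled, or that arms cannot be compared on them at all. SAP 2.6.1.1 and 2.6.1.2 do not support that reading. Nor can it be said that the AE tables will fail to show exacerbations as their own term, because the coding is not in the documents.

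A second reply is that this is an efficacy item and not a deleted safety analysis. The protocol summary lists investigator-determined exacerbation among the efficacy assessments, and Protocol 12.6.1 analyses it under the efficacy heading. This also stands. Its place under treatment of adverse events in Protocol 6.7.2 does not make it a safety endpoint, and the SAP followed the protocol's own classification. A reader might also take exacerbation to be the gravest outcome left unreported. Death is graver, and it is kept both in PFS and in its own summary.

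A third reply is that the change is disclosed, dated before database lock and explained by early termination, in a study that the SAP calls non-registrational, and that the DMC sees unblinded safety data during conduct. All of this is true, and it answers any suggestion of concealment. It does not put the CRF determination into the report. Early termination is also a weak reason for leaving out one simple table when the SAP keeps repeated-measures models for FVC in mL, DLCO and walk distance.

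**Conclusion.** The point holds in a limited form. Both dedicated exacerbation outputs are cancelled, and the investigator's CRF determination by the 2016 criteria is collected but not summarised by arm. Exacerbations remain visible only indirectly, through a hospitalisation component that mixes causes and misses events without admission, and through AE and SAE tables under the coded term.

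The size of the gap is two planned outputs reduced to none, with two partial routes left. The effect on any conclusion cannot be quantified, because neither the event rate nor the actual arm sizes are given. The survival figures in Protocol 1.1 describe prognosis after an event, not the consequence of omitting a table. The verdict assumes that the exacerbation CRF page was completed as the protocol requires, and that the SAP text is followed as written.

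**What to change.** In SAP 2.12 and Section 4, exempt IPF exacerbations from the cancelled analyses, as 2.12 already does for soluble biomarkers. Keep the descriptive summary planned in Protocol 12.6.1, on the participants treated. By arm, report the number and percentage with at least one definite, and with at least one definite or suspected, exacerbation from the CRF determination. Add a listing by participant.

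Protocol 12.6.1 speaks of exacerbations without stating the counting unit. Counting participants, and showing the two categories of Protocol 6.7.2.2, makes the summary specific without adding inference. State in the SAP that the output is descriptive, with no formal test. The planned time-to-event analysis need not be restored.

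The cost is a few lines of SAP text, one table and one listing from data already collected. Treatment, visits and clinical rules do not change.

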## **2.13 Interim analysis**

There will be no interim analysis due to the early termination of the study.

## **3 Sample size calculation**

Refer to Protocol Section 12.8 and Section 17 for Details.

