12.8 Sample size calculation

12.8.1 Primary endpoint(s)

Without considering the drop-off rate, 40 participants per active treatment group and at least 40 participants on placebo of each cohort will give at least 80% power to detect a treatment improvement in change from baseline in FVC%_p (treatment – placebo) for at least 2% in patients with IPF assuming the standard deviation is around 5%.

The sample size calculation is based on the primary efficacy endpoint of change from baseline in FVC%_p at week 26. The criteria for this calculation aimed for a 90% level of proof that difference in change in FVC%_p from baseline to week 26 between treatment and placebo and the mean treatment effect is at least 1.3% better than placebo effect with 50% probability. The former targets proof that the treatment produces a statistically significant improvement in change from baseline in FVC, while the latter targets proof of clinical relevance.

The sample size calculation also takes into account the interim analysis step with futility and early efficacy criteria defined in [Section 12.7](#). The overall type I error at the end of study will be approximately 13%.

Additional participants may be enrolled if more than 15% of the planned randomized participants have not completed the 26 weeks of treatment, as per protocol requirements. Prior to enrolling additional participants, a DMC review of safety data will occur to ensure there are no tolerability/safety issues that would advise against enrolling additional participants.

Refer to [Section 17](#) for cohort specific sample size after considering drop off rate and randomization ratio between the treatment group and placebo group.

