17.1.11 Statistical considerations

17.1.11.1 Sample size calculation

As the first cohort in this platform study, the randomization ratio between the treatment group and placebo group is determined as 1:1. Assuming the drop-off rate of 15% [Raghu et al 2018b](#), 47 patients will be randomized into each treatment group with a total of 94 patients for this cohort. The sensitivity of power to changes in assumptions with different drop off rate is listed in [Table 17-5](#).

Table 17-5 Sensitivity of power to changes in assumptions for N=47 per group

True treatment difference for LTP001 vs Placebo (%)	Power for primary endpoint (type I error around 10%)		
	With 10% drop-out rate (38 per group)	With 15% drop-out rate (40 per group)	With 20% drop-out rate (43 per group)
1.6	64%	65%	65%
1.8	72%	72%	73%
2	79%	79%	80%
2.2	84%	85%	85%
2.4	89%	89%	90%

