**Table 2-2 Composition of the robust weakly informative prior for the placebo tie slope**

|   | Comp1 | Comp2 | Comp3 |
|---|-------|-------|-------|
| W | 0.526 | 0.174 | 0.300 |
| M | -2.93 | -2.75 | -3.00 |
| S | 0.865 | 1.837 | 4.754 |

This effectively means that we assume a placebo decline of 3% at week 26 from the baseline for the placebo group is expected. This prior belief is fixed at the design stage. Any new placebo historical data that becomes available, will not be used as part of a prior. The impact of using this placebo prior means that there would be in effect 11 more placebo participants contributing to the data analysis. A non-informative prior will be used for the rest of the parameters, assuming the change from baseline in FVC%p has a normal distribution with mean=0 and a very large SD (e.g., 1E6).

The primary summary measure of interest is the difference in FVC%p between active and placebo at week 26 derived from the Bayesian statistical model as the posterior mean estimation of the treatment effect over placebo for change from baseline FVC %p at the end of treatment (26 weeks). Statistical evidence of treatment effect will be concluded if the probability that the effect is better than placebo by 90% and there is at least 50% probability that the effect over placebo is >1.3%. No adjustments for multiplicity will be applied for this exploratory study.

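### SAP section 3 still relies on power and type I error that assumed the interim SAP 2.13 cancels; under the planning assumptions, with 40 evaluable per arm, the single final analysis has about 76% power at 2 points and about 8% type I error

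*SAP*

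**What the plan says.** Protocol 12.8.1 states that "40 participants per active treatment group and at least 40 participants on placebo of each cohort will give at least 80% power" to detect an improvement "for at least 2% in patients with IPF assuming the standard deviation is around 5"%. It adds: "The sample size calculation also takes into account the interim analysis step with futility and early efficacy criteria defined in" Protocol 12.7. On error it says: "The overall type I error at the end of study will be approximately 13"%. Table 17-5 (Protocol 17.1.11.1), headed "Power for primary endpoint (type I error around 10"%), gives 79% power at 2 points for 40 per group.

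Protocol 12.7.2 places the interim at about half of the participants. Its early-efficacy criterion is the same two-part rule as at the end: 90% posterior probability of an effect above 0 and 50% of an effect above 1.3 points. Futility is flagged when the posterior probability of an effect below 0 exceeds 60%.

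SAP 2.13 then states: "There will be no interim analysis due to the early termination of the study". SAP 4 lists the planned interim analyses among the items removed. SAP 2.5.2 keeps the primary success rule ("Statistical evidence of treatment effect will be concluded if the probability that the effect is better than placebo by 90"%, plus the 50% condition on 1.3 points). SAP 3 is one line: "Refer to Protocol Section 12.8 and Section 17 for Details".

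**The concern.** An interim look with the same success rule as the final analysis is a second chance to succeed. Counting it raises both power and type I error. Once it is cancelled, only the final look can succeed, so both quantities fall. SAP 3 nevertheless sends the reader to the two-look figures with no qualification, while SAP 2.5.2 still draws a conclusion from the success rule.

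At stake is how the primary result is read. Someone who takes the power from SAP 3 will set a miss against 80% at 2 points, and a success against a 13% false-positive rate. Neither figure belongs to the analysis that will be run.

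**Working it through.** **Inputs.** From Protocol 12.8.1 and Table 17-5: 40 evaluable per arm, SD 5, true difference 1.6 to 2.4 points. From SAP 2.5.2: the success rule, an expected placebo change of -3, and a prior worth about 11 placebo participants. From Table 12-1 (SAP Table 2-2): weights 0.526 / 0.174 / 0.300, means -2.93 / -2.75 / -3.00, SDs 0.865 / 1.837 / 4.754. The prior mean is 0.526(-2.93) + 0.174(-2.75) + 0.300(-3.00) = -2.92. From Protocol 12.7.2: interim at 50% with the rules above.

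**Closed-form checks, single look.**
- Flat prior: SE = 5 × √(2/40) = 1.118. The 90% condition needs an observed difference of 1.2816 × 1.118 = 1.433, which already exceeds 1.3. Power at 2 points = Φ((2 - 1.433)/1.118) = Φ(0.507) = 69%.
- Plain normal prior worth 11 placebo participants, centred on the true placebo change: posterior SD = 5 × √(1/40 + 1/51) = 1.056, threshold 1.2816 × 1.056 = 1.353. The estimate's sampling SD is 5 × √(1/40 + (40/51)²/40) = 1.005. Power = Φ((2 - 1.353)/1.005) = Φ(0.644) = 74%.

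Neither reaches 79% or 80%.

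**Simulation of the documents' rule** (400,000 trials). The week-26 mean in each arm is normal with variance 25/n, and the active arm has a flat prior. For placebo, component k of the prior (weight w, mean m, SD s) updates to precision 1/s² + n/25, with weight proportional to w × N(placebo mean; m, s² + 25/n). Then P(effect > c) = Σ w′ Φ((active mean - μ′ - c)/√(25/n + v′)), where w′, μ′ and v′ are the posterior weight, mean and variance of each placebo component. Success requires at least 0.90 at c = 0 and at least 0.50 at c = 1.3. In the two-look version the same rule is applied at 20 per arm, and the trial stops for futility if P(effect < 0) > 0.60.

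Results with 40 per arm and true placebo change -3:

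| True difference | Table 17-5, 40 per group | Two looks | Final look only | Loss |
|---|---|---|---|---|
| 1.6 | 65% | 65.8% | 60.8% | 5.0 |
| 1.8 | 72% | 73.0% | 68.7% | 4.3 |
| 2.0 | 79% | 79.3% | 75.8% | 3.5 |
| 2.2 | 85% | 84.6% | 81.8% | 2.8 |
| 2.4 | 89% | 88.9% | 86.8% | 2.1 |

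Type I error is 12.1% with two looks and 8.0% with the final look only. With true placebo at the prior mean of -2.92 it is 12.7% and 8.4%, and power at 2 points is 80.1% and 76.6%.

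The two-look version matches the protocol's 40-per-group column within 1 point and comes close to its 13% error rate. With the futility look alone, power at 2 points is 75.4%, so the gain comes from the early-success look.

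**Sensitivity of the single-look power at 2 points.**
- Evaluable per arm: 56% at 20, 62% at 25, 67% at 30, 72% at 35, 78% at 47 (all randomized participants, no dropout).
- SD 4.5 to 5.5: 78% to 70%.
- True placebo change -2: 82%; -4: 64%.

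**The case against.** SAP 3 is a pointer. It states no power itself, and Protocol 12.8.1 remains a true record of how the size was chosen. The cancellation is disclosed in SAP 2.13, in SAP 4 and in the SAP's document history. All of this stands. A reader might infer that the protocol's figures are wrong or that the change is concealed. The documents support neither: the two-look figures reproduce, and the removal is listed openly. What is missing is the statement that the power and error rate depended on the removed step.

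The effect is also small. The loss of 2 to 5 points is less than the spread produced by plausible changes in SD or placebo decline, type I error improves, and the trial is described as exploratory and non-registrational. That stands as well, and limits the weight of the point.

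The two-look match is not a unique identification. A single look with a true placebo change of -2.5 gives 66.8 / 74.0 / 80.0 / 85.2 / 89.3% with 10.9% type I error, also near Table 17-5 and its 10% heading. However, that departs from the 3-point decline the plan assumes, and 12.8.1 says outright that the interim was counted. The interim rule was also to be weighed with other endpoints, whereas the simulation treats it as binding.

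Finally, power quoted after termination can become post-hoc power. That is a fair warning if the observed effect is used. It does not apply to the planned effect sizes.

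**Conclusion.** The point holds as a modest correction. The power and type I error reached through SAP 3 belong to a two-look design that will not be run. Under the planning assumptions the single final analysis has about 76% power at 2 points (61% to 87% over 1.6 to 2.4 points) against a stated 79% to 80%, and about 8% type I error against a stated 13%.

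These figures rest on 40 evaluable per arm, SD 5, a true placebo change of -3, the Table 12-1 prior, and week-26 means in place of the random-slope model, for which the documents give no slope or residual variances. A reader might take 76% as the power the trial will actually have. The documents do not support that: they do not give the number of participants after early termination, and with 30 or 20 per arm the figure is about 67% or 56%. Nor is there any increase in false-positive risk; it falls.

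The type I error in the Table 17-5 heading and that table's dropout labels are separate matters and do not affect this result.

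**What to change.** In SAP 3, keep the reference to Protocol 12.8 and Section 17 as the record of the original planning. Add that the power and type I error there assumed the interim analysis that SAP 2.13 cancels. Then give the single-look figures with their assumptions: at 40 evaluable per arm, SD 5 and a placebo decline of 3, about 61 / 69 / 76 / 82 / 87% power at 1.6 / 1.8 / 2.0 / 2.2 / 2.4 points and about 8% type I error. Give the same figures for the sample size available at database lock, using the planned effect sizes and not the observed effect. In SAP 4, beside the removal of the interim, add one line noting this consequence.

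The cost is a few sentences and a short simulation. No participants are added and the primary analysis does not change. The stated power becomes less favourable and the stated type I error more favourable.
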